8.3 Assignment to Treatment Groups

All eligible subjects will be randomized to receive tipifarnib administered according to one of the following dose regimens:

- Regimen 1: 600 mg bid for 7 days on Days 1-7 in 28 day cycles (i.e. 1 week on / 3 weeks off).
- Regimen 2: 300 mg bid for 21 days on Days 1-21 in 28 day cycles (i.e. 3 weeks on / 1 week off).

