10.9 Adverse Event Reporting Period

The AE reporting period for safety surveillance begins when the subject is included into the study (date of first signature of informed consent) and continues through the study's post-treatment follow-up period, defined as 30 days from the final administration of the study treatment or immediately before initiation of any other anticancer therapy, whichever comes first.

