10.1. Adverse Events

Adverse events will be coded using the latest available version of the Medical Dictionary for Regulatory Activities (MedDRA). Treatment-emergent adverse events are defined as AEs that start on or after the first dose of study drug and within approximately 30 days of the last administration of study drug. AEs will be summarized by the number and percentage of subjects who experienced the event, according to SOC and PT. A subject reporting multiple cases of the same AE will be counted once within each SOC and similarly counted once within each PT. For summaries by maximum severity, each subject will be counted only once under the most severe event.

Unless specified otherwise, the denominator for these calculations will be based on the number of subjects who received at least one administration of tipifarnib regardless of the total number of doses or treatment cycles administered. These conventions will be appropriately modified to calculate AE incidence rates separately for each cycle that study therapy is administered. AE incidence rates may also be calculated based on other measures of subject exposure (e.g., total number of treatment cycles administered). For subjects enrolled prior to Protocol Amendment 3, their AE counts will only be provided in the Total column (Regimen 1 + Regimen 2 + Original Cohort). Regimen 1 and Regimen 2 subjects will be presented separately and in the Total columns.

AE durations will be calculated using all TEAEs. For any AE that is still ongoing at the end of study, we will use the last contact date as the end of AE stop date for calculation the duration of AEs. Median, minimum and maximum of AE durations will be reported.

AEs will also be summarized by NCI-CTCAE version 4.03 severity grade and by relationship to each study drug. Additional summaries may also be provided for SAEs, and events resulting in the permanent discontinuation of therapy. All AEs will be included in individual subject listings.

Hematologic abnormalities reported as AEs that were coded to preferred terms in the Investigations SOC have been pooled with appropriate terms in the Blood and Lymphatic System SOC for tabulation for the following categories:

- Platelet count decreased = Thrombocytopenia;
- Neutrophil count decreased = Neutropenia;
- White blood cell count decreased = Leukopenia;
- Lymphocyte count decreased = Lymphopenia.

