Overall view of TEAEs will be provided, which will include the total number of TEAEs, frequency of subjects with TEAEs, drug-related AEs, SAEs, drug-related SAEs, or death within 30-days within administration of study-drug; and AEs leading to permanent discontinuation of study drug. Additionally, a corresponding overall view of exposure-adjusted AE incidence will be provided, in which the exposure-adjusted incidence rate, is calculated as the mean number of events per treatment cycle, with corresponding 95% confidence intervals.

Summary tables will be provided which present the incidence of TEAEs by SOC and PT; and the incidence of TEAEs by SOC/PT by maximum severity (NCI-CTCAE Grades 1 through 5).

Summary tables will be provided which present the incidence of hematology-related TEAEs by SOC and PT; and the incidence of hematology-related TEAEs by SOC/PT by maximum toxicity grade.

A summary of the AE durations for all TEAEs by SOC/PT will be provided.

Summary tables will be provided which present the incidence of study-drug related TEAEs; and the incidence of study-drug related TEAEs severity scores of Grade 3 or higher.

Summary tables will be provided which present the incidence of SAEs by SOC/PT; and the incidence of TEAEs leading to permanent discontinuation of drug by SOC/PT.

Data on AEs will be presented in listings.

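### SAP 10.1's exposure-adjusted AE rate counts events to about 30 days after the last dose but divides by cycles, so a completed last cycle supplies up to 37 days of events in Regimen 1 and 51 in Regimen 2; add a person-time rate (minor)

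*SAP*

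**What the plan says.** Protocol 8.3 defines the two schedules: "Regimen 1: 600 mg bid for 7 days on Days 1-7 in 28 day cycles" and "Regimen 2: 300 mg bid for 21 days on Days 1-21 in 28 day cycles". The cycle length is the same, and the last dosing day of a completed course differs by 14 days.

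SAP 10.1 defines treatment-emergent events as "AEs that start on or after the first dose of study drug and within approximately 30 days of the last administration of study drug". Protocol 10.9 sets the collection period at "30 days from the final administration of the study treatment or immediately before initiation of any other anticancer therapy, whichever comes first". The SAP definition does not repeat the cut at new anticancer therapy.

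For the overview table, SAP 10.1 specifies one exposure-adjusted incidence rate, which "is calculated as the mean number of events per treatment cycle", with a 95% confidence interval. It does not say how events after the end of the last cycle relate to the denominator, or whether the mean pools all cycles or averages subject-level ratios. The same section adds that "AE incidence rates may also be calculated based on other measures of subject exposure". This is optional, and the only example offered is again the number of cycles.

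SAP 10.1 shows the regimens separately. Protocol 9.4 says the study data will be used to choose the dose and regimen for further development. Neither document describes a formal between-regimen safety test.

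**The concern.** The numerator and denominator of the rate cover different periods. The numerator takes in events from the tail after the last cycle; the denominator stops at the count of cycles. The mismatch would be harmless in a regimen comparison if the tail were equally long in both arms. It is not: beyond Day 28 of a completed last cycle, the window extends 9 days in Regimen 1 and 23 days in Regimen 2.

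Events unrelated to the timing of dosing are plausible here. The overview counts all treatment-emergent events, not only related ones. Eligible subjects have neutrophils below 1000/mm³ (Protocol 7.1), Protocol 5.1 describes death from infection and bleeding in this disease, and Protocol 10.7 has signs and symptoms associated with progression recorded as AEs. Progression is also a listed reason for stopping treatment (Protocol 8.4).

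For such events, part of any excess in Regimen 2 would come from the denominator. Protocol 9.4 introduced the one-week schedule in the expectation that a 3-week rest would reduce myelosuppression, so the error would run in the expected direction, in a rate labelled as already adjusted for exposure.

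**Working it through.** The documents state no figure for AE observation time or AE rate, so there is nothing of the plan's own to reproduce.

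**Inputs.** Cycle length 28 days; last dosing day 7 (Regimen 1) or 21 (Regimen 2), from Protocol 8.3. Window of 30 days after the last dose, from SAP 10.1 and Protocol 10.9. The number of cycles per subject, k, is not given, so a range of 1 to 12 is shown as an assumption. The base case further assumes no cycle delays, a completed last course and no new therapy inside the window.

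**Last cycle, counted from its Day 1.** Regimen 1: 7 + 30 = 37 days, or 37 − 28 = 9 beyond the cycle. Regimen 2: 21 + 30 = 51 days, or 51 − 28 = 23 beyond. The difference is 14 days. After the last dose the count is 30 days in both, a difference of 0.

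**Total observed days.** 28(k − 1) + 37 for Regimen 1 and 28(k − 1) + 51 for Regimen 2. At the same constant daily event rate, events are proportional to observed days while both arms divide by k. The false ratio of per-cycle rates is then the ratio of observed days. The two rate columns assume 1 event per 28 days in both arms.

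| Cycles k | Days, Reg. 1 | Days, Reg. 2 | Ratio 2:1 | Per-cycle rate, Reg. 1 | Per-cycle rate, Reg. 2 |
|---|---|---|---|---|---|
| 1 | 37 | 51 | 1.38 | 1.32 | 1.82 |
| 2 | 65 | 79 | 1.22 | 1.16 | 1.41 |
| 3 | 93 | 107 | 1.15 | 1.11 | 1.27 |
| 6 | 177 | 191 | 1.08 | 1.05 | 1.14 |
| 12 | 345 | 359 | 1.04 | 1.03 | 1.07 |

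Dividing by observed days instead gives a ratio of 1.00 in every row.

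**What reduces the 14 days.** If Regimen 2 dosing stops on Day 14 of the last cycle, the windows end on Days 37 and 44, a difference of 7. If dosing stops by Day 7 in both arms, the difference is 0. If new therapy starts on Day 45, the windows end on Days 37 and 44, again 7. If it starts by Day 38, the difference is 0.

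**The word approximately.** With a 23- or 37-day window the 14 days are unchanged, and the one-cycle ratio becomes 44/30 = 1.47 or 58/44 = 1.32.

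**Events tied to dosing.** If risk is confined to dosing days plus 7, all risk days fall within the 28-day cycle and the tail adds no events in either arm. With dosing days plus 14, the tail adds 0 risk days in Regimen 1 and 7 in Regimen 2 (Day 35 against Day 28).

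**Pooled or averaged.** Suppose half the subjects have 1 cycle and half have 6 (assumption), with 1 event per 28 days. Pooled: Regimen 1 (37 + 177)/7/28 = 1.092, Regimen 2 (51 + 191)/7/28 = 1.235, ratio 1.13. Averaged subject ratios: Regimen 1 (37/1 + 177/6)/2/28 = 1.188, Regimen 2 (51/1 + 191/6)/2/28 = 1.479, ratio 1.25.

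**The case against.** The strongest reply is that the 14 days are not surplus follow-up. Regimen 2 subjects are still taking drug on Days 8–21, and both arms are then followed for 30 days. An event on Day 40 is 33 days after the last dose in Regimen 1 and 19 days after it in Regimen 2; a definition tied to the last dose is meant to separate these. That stands. A reader might infer from 37 against 51 days that Regimen 2 is followed longer after treatment; the documents do not support this.

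A second reply is that events per cycle delivered is a legitimate quantity, and that person-time has its own fault. If risk is confined to dosing days plus 7, a one-cycle subject has 14 risk days in Regimen 1 and 28 in Regimen 2, a per-cycle ratio of 2.0. Dividing by 37 and 51 days reports 2.0 × 37/51 = 1.45 and dilutes a real difference. Protocol 5.5.2 says enzyme inhibition reverses within 3 to 7 days of stopping, so this pattern is credible for drug toxicity. This also stands: neither denominator suits every event type, which is why both rates should be shown.

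Third, the SAP has partial safeguards: incidence by cycle, tables of drug-related events, laboratory-graded hematological toxicity and full listings. Non-final, undelayed cycles have 28 days in both arms. Precision is also low. With 18 subjects of 3 cycles each and a Poisson count, a Regimen 1 rate of 1.11 has a 95% interval of about 1.11 ± 1.96 × √59.8/54, or 0.83 to 1.39, which contains the 1.27 for Regimen 2. These points limit the consequence. They do not align the numerator with the denominator.

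**Conclusion.** The mismatch is real and specific to the exposure-adjusted rate in SAP 10.1. For events at a constant rate unrelated to dosing, with a 30-day window, a completed last course and no new therapy inside the window, the Regimen 2 per-cycle rate is inflated relative to Regimen 1 by 38% at 1 cycle, 15% at 3, 8% at 6 and 4% at 12. Under that window these are maxima. The realised size cannot be stated, because the documents give neither cycle counts nor the timing of events.

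A reader might go further and conclude that the plan biases the safety comparison toward Regimen 1. The documents do not support that as a general statement: it depends on events not being clustered around dosing, the tail enters only once per subject, and the comparison is descriptive. The go/no-go rule rests on response rate within each cohort, not on this rate. Severity is minor. The change is still worth making, because this is the only exposure adjustment the SAP specifies and Protocol 9.4 says the data will inform the choice of regimen.

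**What to change.** In SAP 10.1, keep the per-cycle rate and report beside it, by regimen, treatment-emergent events per 28 days of subject-time at risk, with a 95% confidence interval. Time at risk runs from first dose to the earliest of last dose plus 30 days, start of other anticancer therapy, death or last contact; the numerator should use the same end point. One added sentence should say whether the per-cycle mean is pooled or averaged over subjects.

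Do not try to equalise the arms by counting only through Day 37 of the last cycle. That would leave Regimen 2 with 37 − 21 = 16 days after its last dose against 30 in Regimen 1, and would discard Regimen 2 events 17 to 30 days after dosing.

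The cost is SAP wording and a small programming change using dosing, subsequent-therapy and survival data that the study already collects. The downside is one more descriptive rate, which can dilute a real regimen difference when events cluster around dosing. The two rates should therefore be read together.

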10.2. Clinical Laboratory Evaluations

Hematological toxicities Grade 3 or above based on NCI-CTCAE version 4.03 criteria will be summarized across all treatment cycles. A shift table will be presented for the shift from baseline to worst post-baseline severity grade. Severity grading is based on the National Cancer Institute Common Terminology Criteria for Adverse Events (CTCAE), version 4.03, with normal ranges defined from the American Medical Association Standard Lab Normal Ranges. For laboratory values that fall outside the defined severity ranges, a value of 0 was entered. Not Applicable is given to those laboratory values that have no associated CTCAE severity criteria.

The data for clinical laboratory evaluations (including hematology, chemistry, coagulation, and pregnancy testing) will be presented in listings. In addition to the results, these listings will present the normal range, toxicity grade, and clinical assessment (Normal; Abnormal, but not clinically significant; Abnormal, clinically significant) associated with evaluations.

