Two dosing regimens will be tested based on the prior experience with tipifarnib in patients with MDS (see Section 9.4), each employing a Simon two stage design. This design was selected in order to minimize the number of study subjects treated if tipifarnib were considered not sufficiently efficacious to grant further development in this subject population. As part of Amendment 3, eligibility criteria have been modified to include subjects with baseline neutrophils < 1000/mm3 and platelets > 20,000/mm3 based on the review by the Sponsor of data from a prior trial of tipifarnib in subjects with intermediate and high risk MDS (Fenaux 2007). In brief, in study INT-28, subjects with peripheral neutrophil counts >1000/mm3 and platelet counts < 20,000/mm3 appeared less likely to receive clinical benefit from tipifarnib therapy. These results may reflect the known effects on neutrophil bone marrow homing (J Innate Immun 2013; 5:304-314) and platelet production (Blood 2012; 120:2775-6. 24) of the CXCL12/CXCR4 pathway, recently identified as a target of tipifarnib (http://www.kuraoncology.com/wp-content/uploads/2017/06/KO-TIP-002-EHA-2017-Poster-v2017-06-01-FINAL.pdf). A relationship between CXCL12/CXCR4 expression, hematology parameters and outcome of tipifarnib therapy will be investigated as an exploratory aim of the present study.

Page 25 of 79

Thus the assessment of the effect of tipifarnib in MDS is warranted.

The rationale for the selection of the dose and treatment regimen is provided in Section 9.4.

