7 SUBJECT SELECTION

7.1 Inclusion Criteria

For inclusion of a subject in the study, all of the following inclusion criteria must be fulfilled:

- 1. Subject is at least 18 years of age.
- 2. Documented pathological evidence of MDS as defined by the WHO criteria (Table 8).
- 3. Eastern Cooperative Oncology Group (ECOG) performance status 0, 1 or 2.
- 4. Subjects have no known curative treatment.
- 5. Subject is willing and able to comply with scheduled visits, treatment plans, laboratory tests and other procedures (including bone marrow assessments).
- 6. At least 1 week since the last systemic therapy regimen prior to Cycle 1 Day 1. Subjects must have recovered to NCI CTCAE v. 4.03 < Grade 2 from all acute toxicities (excluding Grade 2 toxicities that are not considered a safety risk by the Sponsor and Investigator) or toxicity must be deemed irreversible by the Investigator.
- 7. Acceptable hematological function:
 - a. Absolute neutrophil count < 1000/mm³
 - b. Platelet count > 20,000/mm³
- 8. Acceptable liver function:
 - a. Total or direct bilirubin \leq 1.5 x ULN; does not apply to subjects with Gilbert's syndrome diagnosed as per institutional guidelines.
 - b. AST (SGOT) and ALT (SGPT) $\leq 2.5 \text{ x ULN}$.

- 9. Acceptable renal function with serum creatinine ≤ 1.5 x ULN or a calculated creatinine clearance ≥ 60 mL/min using the Cockcroft-Gault or Modification of Diet in Renal Disease formulas
- 10. Female subjects must be:
 - a. Of non-child-bearing potential (surgically sterilized or at least 2 years post-menopausal); or
 - b. If of child-bearing potential, subject must use a highly effective method of contraception, such as combined (estrogen and progestogen containing) hormonal contraception associated with inhibition of ovulation, progestogen-only hormonal contraception associated with inhibition of ovulation, intrauterine device, intrauterine hormone-releasing system, bilateral tubal occlusion, vasectomised partner or sexual abstinence. Both females and male subjects with female partners of child-bearing potential must agree to use a highly effective method of contraception for 2 weeks prior to screening, during, and at least 4 weeks after last dose of trial medication. Female subjects must have a negative serum or urine pregnancy test within 72 hours prior to start of trial medication.
 - c. Not breast feeding at any time during the study.
- 11. Written and voluntary informed consent understood, signed and dated.

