10.7 Events Not to Be Considered as AEs/SAEs

Medical conditions that are present at the initial study visit that do not worsen in severity or frequency during the study are defined as Baseline Medical Conditions and are NOT to be considered AEs. Progression of underlying disease is not an AE and therefore not an SAE per se, rather an efficacy end-point, unless deemed to be causally related to administration of IPs. However, if adverse signs or symptoms occur in association with disease progression then these should be recorded as AEs and reported as SAEs if meeting any seriousness criteria.

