12.2.2 Safety and Tolerability

Safety and tolerability of tipifarnib will be assessed based on the following:

- Incidence, duration, and severity of TEAEs, SAEs, AEs resulting in permanent discontinuation of study drug, and deaths within approximately 30 days from the last dose of study drug (or immediately before the administration of another anticancer treatment)
- Changes in laboratory test results

AEs will be coded using the latest available version of the Medical Dictionary for Regulatory Activities (MedDRA). TEAEs are defined as AEs that start on or after the first dose of study

drug and within approximately 30 days of the last administration of study drug. AEs will be summarized by the number and percentage of subjects who experienced the event, according to system organ class and preferred term. A subject reporting multiple cases of the same AE will be counted once within each system organ class and similarly counted once within each preferred term

Unless specified otherwise, the denominator for these calculations will be based on the number of subjects in each cohort who received at least one administration of tipifarnib, irrespective of the total number of doses or treatment cycles administered. These conventions will be appropriately modified to calculate AE incidence rates separately for each cycle that study therapy is administered. AE incidence rates may also be calculated based on other measures of subject exposure (e.g., total number of treatment cycles administered). AEs will also be summarized by NCI CTCAE v.4.03 severity grade, by relationship to each study drug and by treatment regimen. Additional summaries may also be provided for SAEs, and events resulting in the permanent discontinuation of therapy. All AEs will be included in individual subject listings.

The incidence of grade 3 and 4 hematological toxicities (including neutropenia, thrombocytopenia, and anemia) will be provided by treatment cycle and across all treatment cycles. The toxicity grades for laboratory tests will be based on NCI CTCAE v.4.03 criteria. The use of blood transfusions (platelets, red blood cells, whole blood) and/or growth factor support will be reported.

Vital sign results (heart rate, blood pressure and temperature) will be summarized descriptively for each scheduled and unscheduled protocol time point. Changes will be calculated relative to the assessments at baseline.

Sample Size Determination

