10. SAFETY ANALYSES

Safety and tolerability of tipifarnib will be assessed based on the following:

- Incidence, duration and severity of TEAEs, SAEs, AEs resulting in permanent discontinuation of study drug, and deaths within approximately 30 days from the last dose of study drug (or immediately before the administration of another anti-cancer treatment)
- Changes in laboratory test results
- Serum Chemistry: Blood Urea Nitrogen, Creatinine, Potassium, Calcium, Total Bilirubin, ALT, AST
- Hematology: White Blood Cell Count, Hemoglobin, Platelet Count, Absolute Neutrophil Count, Neutrophil Precursors (promyelocytes, myelocytes, metamyelocytes, band neutrophils), Lymphocytes, Monocytes, Blasts, and Reticulocytes.
- Coagulation panel: PT/INR, APTT
- Changes in vital signs: blood pressure, heart rate, temperature

Unless explicitly indicated otherwise, all analyses for safety will be based on the ASaT population.

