13. DATA HANDLING CONVENTIONS

Analyses will be performed using SAS® [SAS Institute 2011] Version 9.3 or higher.

The clinical database will be locked prior to the initiation of the Stage 1 statistical analyses. A database lock is defined as a stable database that can be analyzed and reported. Changes to a locked database must be authorized in writing by the study sponsor [REDACTED]

The data conventions include the following.

- Data will be described and summarized by study stage (Stage 1 or Stage 2), Stage 1 cohort (starting dose level and schedule), or Stage 2 cohort (disease type).
- Summary tables for continuous variables will contain the following statistics: N (number of subjects in the population); n (number of subjects with data for that variable); mean; standard deviation; median; minimum; and maximum. Selected statistics may also include 2 sided 95% normal approximation confidence intervals (CI) on the mean.
- Summary tables for categorical variables will include: N (number of subjects in the denominator); n (number of subjects in the numerator); and percent. Selected statistics also may include 2-sided 95% CIs for the percent, calculated using the CL=AGRESTICOULL option in SAS PROC FREQ.

- The baseline value for a given parameter is the last value prior to the first dose. A value is considered to be post-baseline if it is obtained after the first dose. A value is considered to be postdose on a given cycle day if it is obtained after the dose is administered on that day.
- Data from all study centers will be pooled for all analyses.
- Unless otherwise specified, statistical testing will be 2-sided at a nominal 0.05 level of significance.
- Study day is defined as calendar date – date of first treatment + 1 if the calendar date is on or after the date of first treatment, and calendar date – date of first treatment if the calendar date is before the date of first treatment
- Measurements from unscheduled visits will be included in listings, but not summary tables.
- Missing data conventions for individual endpoints are described in the SAP section for the endpoint.
- Additional exploratory analyses may be performed as deemed appropriate after review of the pre-specified analyses. Log-transformations or nonparametric tests may be applied to measurements displaying a significant degree of non-normality.
- Listings will be provided for all data collected in the eCRF.

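### The grade 3+ laboratory neutropenia summary takes no account of baseline grade, although entry requires a neutrophil count below 1000/mm³

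*SAP*

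**What the plan says.** **Entry.** Protocol 7.1, criterion 7a, requires "Absolute neutrophil count < 1000/mm³". This is an upper limit with no lower one. It is deliberate: Protocol 5.6 explains that under Amendment 3 "eligibility criteria have been modified to include subjects with baseline neutrophils < 1000/mm3 and platelets > 20,000/mm3".

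**Laboratory summary.** Protocol 12.2.2: "The incidence of grade 3 and 4 hematological toxicities (including neutropenia, thrombocytopenia, and anemia) will be provided by treatment cycle", and also across all cycles. SAP 10.2: "Hematological toxicities Grade 3 or above based on NCI-CTCAE version 4.03 criteria will be summarized across all treatment cycles". Neither sentence refers to baseline. SAP 8 leaves subjects enrolled before Amendment 3 out of tables unless noted, so this summary should hold mainly subjects who entered under the neutrophil criterion.

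**Baseline elsewhere.** The next sentence of SAP 10.2 does use baseline: "A shift table will be presented for the shift from baseline to worst post-baseline severity grade". SAP 13 defines it: "The baseline value for a given parameter is the last value prior to the first dose". SAP 10 also lists "Changes in laboratory test results" among the safety measures.

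**Adverse events.** Protocol 10.7 takes out of adverse event reporting "Medical conditions that are present at the initial study visit that do not worsen in severity or frequency during the study". Protocol 10.4 generally keeps isolated laboratory abnormalities out as well, and SAP 10.1 requires treatment-emergent events to start on or after the first dose.

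**The concern.** A toxicity incidence is meant to show what happened under treatment. When the entry criterion places subjects in the category being counted, and the count does not ask for a change from baseline, the figure mostly describes who was enrolled.

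Myelosuppression matters to this trial's purpose. Protocol 9.4 gives it as the reason for the Amendment 2 schedule change and says the data will be used to choose a dose and regimen for further development. A neutropenia rate held near its upper limit in both cohorts cannot inform that choice and could be misread as severe toxicity in most subjects. The adverse event tables do not fill the gap, because an asymptomatic fall in neutrophils will usually not be reported as an adverse event under Protocol 10.4.

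**Working it through.** The documents state no expected neutropenia rate, so there is no planned figure to reproduce.

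**Inputs from the documents**
- Neutrophil count below 1000/mm³ at entry (Protocol 7.1).
- Hematology on Day 1 of each cycle, with a Day 22 visit only in Cycles 3, 6, 9, 12 and every third cycle after (Protocol Table 1). Most cycles therefore have one scheduled count.
- Unscheduled values go to listings, not summary tables (SAP 13).

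**Assumptions, not in the documents**
- CTCAE v4.03 grade 3 neutrophils: below 1000 to 500/mm³; grade 4: below 500/mm³.
- On-study counts are log-normal and independent between visits, with mean 700 or 900/mm³, within-subject CV 20% to 40%, and no drug effect.

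**Step 1. Chance that a subject scores with no drug effect.** Let q be the probability that one count is below 1000/mm³, with σ² = ln(1 + CV²) and q = Φ[(ln 1000 − ln mean + σ²/2)/σ]. Over k counts, P(at least one) = 1 − (1 − q)^k.

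| Mean count | CV | q | k = 3 |
|---|---|---|---|
| 700 | 20% | 0.971 | 1 − 0.029³ > 0.999 |
| 700 | 30% | 0.913 | 1 − 0.087³ = 0.999 |
| 700 | 40% | 0.868 | 1 − 0.132³ = 0.998 |
| 900 | 20% | 0.736 | 1 − 0.264³ = 0.982 |
| 900 | 30% | 0.693 | 1 − 0.307³ = 0.971 |
| 900 | 40% | 0.679 | 1 − 0.321³ = 0.967 |

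**Step 2. If counts often recover.** With q = 0.3, three counts give 1 − 0.7³ = 0.66 and six give 0.88. With q = 0.5, the values are 0.88 and 0.98. The ceiling is softer, but repeated counting across cycles still pushes the figure up.

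**Step 3. Response of the crude incidence to the drug.** Let b be the share already at grade 3+ at baseline, and d the chance of new grade 3+ in the rest. If each subject in b has at least one later low value, crude incidence = b + (1 − b)d. A difference in d between regimens shows up only as (1 − b) times that difference.

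| b | d = 0 | d = 10% | d = 60% | Visible gap, d = 10% vs 60% |
|---|---|---|---|---|
| 100% | 100% | 100% | 100% | 0 points |
| 90% | 90% | 91% | 96% | 5 points |
| 80% | 80% | 82% | 92% | 10 points |
| 50% | 50% | 55% | 80% | 25 points |

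The last row shows what a lower grade 3 cut-off could do: the problem shrinks but remains. A move from grade 3 to grade 4 adds nothing to the crude figure in any row.

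**Step 4. Which values count.** The shift-table sentence says post-baseline; the incidence sentence does not. In Cycle 1 the only scheduled count is the Day 1 count, taken before the first dose. If values were assigned by visit cycle, the by-cycle incidence in Protocol 12.2.2 could show baseline as Cycle 1 toxicity. The text neither says nor excludes this.

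**The case against.** The strongest reply is that the remedy is largely planned. The shift table gives the number moving from grade 3 to grade 4, the denominator for it, and the number already at grade 4. The crude summary is one descriptive display, with no hypothesis, threshold or stopping rule attached, and its layout belongs to companion shells that are not part of these documents. All of this stands, and it limits the importance of the point. It does not change what the incidence sentence says: baseline is used in one sentence of SAP 10.2 and not in the one before it.

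Three stronger readings are tempting, and the documents do not support them.

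- *The safety endpoint is compromised.* SAP 10 to 10.3 plan many displays that do not count unchanged baseline values: treatment-emergent, drug-related and serious events, discontinuations, transfusion and growth factor use.
- *Every subject starts at grade 3 or worse and the rate will be 100% whatever the drug does.* Screening hematology is at least a week before Cycle 1 Day 1 and is repeated before dosing, so the baseline value can differ from the qualifying one. Counts may also rise on study: hematologic improvement is part of the primary response. Within a cycle that has one count, Step 1 gives q of 0.68 to 0.97, so a by-cycle figure has room to move, and a separate grade 4 row could still distinguish the regimens.
- *The rate will look far worse than the 18% grade 3-4 neutropenia in Protocol 5.5.3.* That is a treatment-related adverse event rate. Its counterpart here is the drug-related grade 3+ event table in SAP 10.1, not the laboratory summary.

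The missing baseline condition also applies to platelets and hemoglobin. How many subjects would enter at grade 3 for those cannot be derived from the documents, so no size is claimed.

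**Conclusion.** The point holds for the grade 3+ laboratory summary. As written, the across-cycles neutropenia incidence would be driven mainly by the entry criterion and would say little about drug effect or the contrast between regimens, unless counts often recover.

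Its size under no drug effect is 97% to over 99.9% per subject over three counts at mean counts of 700 to 900/mm³, and 66% to 88% if the per-visit probability of a low count is only 0.3 to 0.5. This rests on the assumed CTCAE cut-off, the assumed means and CVs, and independence between visits. The absence of a worsening condition does not depend on any of these; only the size does. The shift table means the information is not lost, so this is a correction to a table definition and not a flaw in the trial's inference.

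**What to change.** In SAP 10.2 and Protocol 12.2.2, count a laboratory hematological toxicity only when a post-baseline value is grade 3 or 4 and at least one grade worse than the baseline defined in SAP 13. For neutrophils, report the proportion moving to grade 4 among subjects at grade 3 or better at baseline, and state how many were already at grade 4. Keep the shift table and make it the main display for neutropenia. Align the table shells.

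The same edit can settle a related gap. Protocol 12.2.2 promises the incidence by cycle as well as overall, SAP 10.2 keeps only the overall version, and SAP 15 declares no changes. Either restore the by-cycle table, using values after the first dose only, or list its removal in SAP 15.

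The cost is wording and one derived flag. The baseline grades are already needed for the shift table, and no new data are collected. The downside is that subjects at grade 4 at baseline cannot score and leave the neutrophil denominator, which is why their number must be shown.
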